## LIST OF ABBREVIATIONS AND RELEVANT DEFINITIONS

ABR ABR form, General Assessment and Registration form, is the application

form that is required for submission to the accredited Ethics Committee (In

**Dutch, ABR = Algemene Beoordeling en Registratie)** 

AE Adverse Event

AR Adverse Reaction

**CA** Competent Authority

CCMO Central Committee on Research Involving Human Subjects; in Dutch:

**Centrale Commissie Mensgebonden Onderzoek** 

CV Curriculum Vitae

**DSMB** Data Safety Monitoring Board

**EU** European Union

**EudraCT** European drug regulatory affairs Clinical Trials

**GCP** Good Clinical Practice

IB Investigator's Brochure

IC Informed Consent

IMP Investigational Medicinal Product

IMPD Investigational Medicinal Product Dossier

METC Medical research ethics committee (MREC); in Dutch: medisch ethische

toetsing commissie (METC)

(S)AE (Serious) Adverse Event

SPC Summary of Product Characteristics (in Dutch: officiële productinfomatie

IB1-tekst)

Sponsor The sponsor is the party that commissions the organisation or performance

of the research, for example a pharmaceutical

company, academic hospital, scientific organisation or investigator. A party

that provides funding for a study but does not commission it is not

regarded as the sponsor, but referred to as a subsidising party.

SUSAR Suspected Unexpected Serious Adverse Reaction

Wbp Personal Data Protection Act (in Dutch: Wet Bescherming Persoonsgevens)

WMO Medical Research Involving Human Subjects Act (in Dutch: Wet Medisch-

wetenschappelijk Onderzoek met Mensen

**BoNT** Botulinum neurotoxin

CGI Clinical Global Impression scale

**EMG** Electromyogram

EEG Electroencephalogram

NSAID Non steroidal anti-inflammatory drug

**UMRS** Unified Myoclonus Rating Scale

ALDS AMC Linear Disability Scale

SF-36 Short form-36

MINI Mini International Neuropsychiatric Interview

PUTS Premonitory Urge for Tics Scale

**CRU** Clinical Research Unit

MRC Medical Research Counsil

## **SUMMARY**

Rationale: Botulinum neurotoxin (BoNT) has emerged as a useful therapy for several movement disorders associated with muscle overactivity such as dystonia and jerky movement disorders. At least 2–9% of patients seen in movement disorder clinics suffer from movement disorders with a psychogenic origin and a substantial part of them has jerks. These psychogenic jerky movement disorders cannot be accounted for by a known neurologic syndrome. Therapy of psychogenic jerks currently focuses on frequently co-occurring psychiatric disease, but results are poor. In this project, we will study the effect of BoNT on movement disorders of psychogenic origin.

**Objective**: To evaluate the effect of treatment with BoNT on psychogenic jerks.

**Study design:** A monocenter study consisting of two parts: a double-blind randomized placebo controlled intervention study of 16 weeks and an uncontrolled follow-up study of one year to evaluate the long-term effects of BoNT.

**Study population:** Patients with at least one invalidating consistent type of psychogenic jerk that is present for 1 year or longer.

**Intervention**: During the trial phase of the study, patients will receive two BoNT or placebo injections with an interval of 3 months. The number of muscles injected and the doses to be administrated in an individual patient will be determined by an experienced neurophysiologist analogous to treatment of dystonia. Hereafter, for the follow-up study all patients will receive 4 BoNT injections at intervals of 3 months. **Main study parameters/endpoints:** 

Primary outcome measure: To assess whether treatment with BoNT leads to improvement of psychogenic jerks according to an independent movement disorder specialist assessed with the Clinical Global Impression - Improvement scale.

Secondary outcome measures are the effect of BoNT on: the severity of jerks according to a movement disorder specialist; improvement and severity of the jerk according to the patient; nature and severity of overall dyskinesia; jerk frequency; whether patients consider treatment with BoNT effective; disability; quality of life; co-existent psychiatric disorders and the occurrence of adverse reactions; muscle weakness. Additionally in approximately 16 patients a resting state fMRI will be performed before and after the treatment intervention (16 weeks after start of the treatment). Analysis of the comparison before and after treatment will be done by a researcher blinded for the intervention.

Nature and extent of the burden and risks associated with participation, benefit and group relatedness:

The risks associated with participation in this study are low: BoNT is considered a safe therapy in other movement disorders. The most common side effects of BoNT are local weakness and pain and side effects are reversible. The neuropsychological and psychiatric questionnaires used in our study are considered to be mildly psychologically stressful.

Functional magnetic resonance imaging is a non-invasive and safe procedure and is very commonly used in clinical practice and research.

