## 4. STUDY POPULATION

## 4.1 Population

Patients with one or more jerks of psychogenic origin that significantly disable them in their daily functioning will be included in the study. Patients will be recruited in several manners. The patients with psychogenic jerks enrolled in an ongoing study focussing on the pathophysiology of jerky movement disorders will be evaluated for eligibility, (METC number 07/290) suitable patients from our outpatient clinic will be asked to participate and movement disorder specialists from other clinics will be asked to refer suitable patients.

Approximately 16 of the 54 patients participating in the BonT study will be included to take part in the fMRI study. These patients will be included at the UMC Groningen and will be included, irrespective of the randomised group that they're in. Furthermore 16 healthy control subjects will be included. Controls need to be healthy, both neurological and psychiatric, and are age- and gender- matched with the participants with psychogenic movement disorder. Controls on medication that affect the brain (like benzodiazepines/opiates/barbiturates) or with a history of substance abuse are excluded from this study.

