# 6.7 Preparation and labelling of Investigational Medicinal Product

Dysport® and placebo will be prepared, blinded and labelled by Ipsen BV, a pharmaceutical company that works according to GMP guidelines. The medication will be transported to the pharmacy of the Academic Medical Center, where it will be checked and approved. To remain double blind the local pharmacy of the Academic Medical Center will prepare botulinum toxin or placebo, according to the dosage determined by the neurophysiologist, for the individual patients according to a randomization list. This is necessary because BoNT is may only be stored for up to 8 hours following reconstitution. The syringes will not contain

information on the allocated treatment. This way the person that performs the injection, the patients and other persons involved in the trial, will remain blind for the supplied therapy.

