## 7.2 Randomisation, blinding and treatment allocation

Patients will be randomized using a central web-based and validated computer program (ALEA) made available by the Clinical Research Unit(CRU) in the AMC. Randomisation will be stratified by type of psychogenic jerks (in extremity vs. abdominal jerks), using variable permuted blocks.

Randomisation lists will be handed by the CRU to the AMC pharmacy, who will safeguard the code. If needed, the randomization code can be broken by the pharmacy. Neither the subject, nor the investigator is informed about allocated therapy. Serious adverse events like life-threatening side-effects, will be an indication for breaking the code for that specific subject. Non-serious adverse events will be treated, but will not be an indication for breaking the randomization code

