## **10 ETHICAL CONSIDERATIONS**

# 10.1 Regulation statement

The study will be conducted according to the principles of the Declaration of Helsinki (version of 2008) and in accordance with the Medical Research Involving Human Subjects Act (WMO) and other guidelines, regulations and Acts. Data management, monitoring and reporting of the study will be performed in accordance with the ICH GCP guidelines. Technicians and data managers of the AMC Clinic Research Unit (CRU) will perform central data management using Oracle Clinical. Internet-based remote data capture will be used for entering, managing and validating data from the investigative sites. Oracle Clinical was designed to meet industry regulations, including: FDA 21CFR Part 11 Rule (1997), ICH; Good Clinical Practice: Consolidated Guideline (1997), and FDA Guidance for Industry "Computerized Systems Used In Clinical Trials" (1999).

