## 10.2 Recruitment and consent

Patients will be recruited in several manners. First, the 20 patients with psychogenic jerks enrolled in an ongoing study focussing on the pathophysiology of jerky movement disorders will be evaluated for eligibility. Furthermore, suitable patients from our outpatient clinic will be asked to participate. Finally, movement disorder specialists from other clinics will be asked to refer suitable patients.

We will only ask those patients who did not object to being contacted for participation in clinical research. Possible subjects will receive an information letter and reply form by mail beforehand. Subjects who are willing possibly participate, are invited for an interview with the investigator at the hospital. Informed consent form will be signed by the subject in presence of the investigator. All patients that will be included in the BoNT treatment study at the UMC Groningen will be asked to participate in the fMRI study. Healthy controls will be recruited using flyers.

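### The fixed primary test ignores the jerk-type strata used in randomisation, and the single-centre label conflicts with enrolment at a second hospital

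*Protocol*

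**What the plan says.** **Number of centres.** The Summary calls the project "A monocenter study consisting of two parts". Section 4.1 says of the roughly 16 fMRI patients, who are a subset of the 54 randomised: "These patients will be included at the UMC Groningen and will be included, irrespective of the randomised group that they're in". Section 10.2 goes further: "All patients that will be included in the BoNT treatment study at the UMC Groningen will be asked to participate in the fMRI study". Section 10.1 adds, in a general description of the data system: "Internet-based remote data capture will be used for entering, managing and validating data from the investigative sites".

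**Operations.** Sections 6.7 and 6.8 have the AMC pharmacy prepare each patient's syringes, because the product "may only be stored for up to 8 hours following reconstitution". Section 7.2 places the randomisation lists and code with the same pharmacy. Section 7.6 brings withdrawn patients back to the AMC. No section gives an injection site for patients entered at Groningen.

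**Randomisation and analysis.** Section 7.2: "Randomisation will be stratified by type of psychogenic jerks", extremity versus abdominal, in variable permuted blocks. Section 9.2 compares the two response proportions with a chi-square or Fisher's exact test and mentions no strata. Section 9.3 provides regression adjustment only where important baseline variables turn out to differ between the arms.

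**The concern.** Two things do not fit together.

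First, a trial that enters patients at a second hospital is not single-centre as far as enrolment goes. The reader cannot tell how many hospitals enrol, how many inject, or whether hospital plays any part in the analysis.

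Second, the primary analysis does not follow the randomisation. Jerk type was presumably chosen as a stratum because it was thought to predict response. Stratifying on a prognostic factor makes the arms more alike than simple randomisation would, so the true variance of the treatment difference falls. An unstratified test still uses the larger variance. It is then conservative, and the precision bought by stratifying is lost. Section 9.3 does not repair this: its trigger is observed imbalance, and jerk type is the variable that the randomisation keeps balanced.

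At stake is power in a trial of 54 patients, and a clear account of where patients enter the trial.

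**Working it through.** **1. The plan's own figure.** Section 4.4: proportions 0.30 and 0.70, two-sided 0.05, chi-square test, 80% power. The usual formula without continuity correction gives 24 per arm (power 0.812). Then 24/0.90 = 26.7, so 27 per arm and 54 in total. The stated size reproduces and is not in dispute. At 27 per arm the same formula gives power 0.857.

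**2. The label against the text.**

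| Topic | Section | Content |
|---|---|---|
| Centres | Summary | one |
| Entry of fMRI patients | 4.1 | at Groningen |
| Entry into the treatment study | 10.2 | some at Groningen |
| Data sources | 10.1 | sites, plural (possibly generic wording) |
| Preparation, code, withdrawal visit | 6.7, 6.8, 7.2, 7.6 | AMC only |
| Place of injection for Groningen patients | none | not stated |

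Section 10.2 concerns entry into the treatment study, not merely a scan, so the single-centre label is wrong for enrolment. For injection the text is silent.

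**3. Cost of ignoring the strata.** The documents give no response rates by jerk type or hospital, so the following are assumptions:
- 54 patients, with 27 or 18 of them in one jerk-type stratum;
- permuted blocks of 2, 4 or 6 within jerk type;
- 16 patients from the second hospital, allocated without regard to hospital;
- overall response 0.50, with additive differences of 30, 40 or 50 points by jerk type and 20 points by hospital, probabilities truncated to 0.01–0.99;
- treatment effect 0 or 40 points (0.30 versus 0.70 on average).

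Each setting had 10,000 simulated trials. Monte Carlo standard errors are about 0.2 points for type I error and at most 0.4 points for power. The comparison is the chi-square test without continuity correction against a Cochran-Mantel-Haenszel (CMH) test stratified by jerk type. Each cell gives the results for 27 and for 18 patients in the stratum.

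| Jerk-type / hospital difference | Type I, chi-square | Type I, CMH | Power, chi-square | Power, CMH |
|---|---|---|---|---|
| 0 / 0 | 4.6%, 3.9% | 4.6%, 3.9% | 84.2%, 84.5% | 84.4%, 84.8% |
| 30 / 20 | 3.5%, 3.8% | 4.8%, 5.2% | 85.8%, 83.2% | 89.7%, 87.1% |
| 40 / 20 | 2.8%, 3.0% | 5.2%, 5.1% | 84.1%, 83.1% | 90.6%, 89.0% |
| 50 / 20 | 1.9%, 2.2% | 4.8%, 5.0% | 82.9%, 83.1% | 92.8%, 91.7% |

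The gain in power is about 4 points at a 30-point jerk-type difference, about 6 at 40 points and 9 to 10 at 50 points. Fisher's test is more conservative still, at 1.0 to 2.0% in the last three rows. Adding hospital as a second CMH stratum changes power by no more than about 1 point either way in these settings.

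**4. Size of chance imbalance by hospital.** If 16 of 54 come from the second hospital, the number allocated to BoNT is approximately hypergeometric (54, 16, 27). P(5 or fewer, or 11 or more) = 2 × 0.0675 = 0.135. With 10 such patients, a difference of 6 or more between arms has probability 0.076; with 20 it is 0.158. Under the assumed 20-point hospital effect, an 11:5 split shifts the treatment difference by 6/27 × 0.20 = 0.044. The standard error of that difference at 27 per arm is √(2 × 0.30 × 0.70/27) = 0.125 at the planned rates, and √(2 × 0.25/27) = 0.136 with both rates at 0.50.

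**The case against.** **The unstratified test is valid.** It does not inflate false positives, and chance imbalance under 1:1 randomisation is already covered by its error rate. This stands: the loss is in power, and only if jerk type predicts response.

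**The statistical analysis plan may refine this.** It is not shown, and a hospital term could sit there, so the lack of one is not in itself a fault. But the protocol does not leave the primary test open. It names one, and that test does not match its own randomisation.

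**Hospital differences are already limited.** One blinded researcher rates the primary outcome from video in all patients (section 7.1.1), so differences between raters at two hospitals cannot arise. Section 9.3 could also pick up a visible hospital imbalance. Both points stand, and they are why hospital takes second place to jerk type here.

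**Stronger readings.** A reader might infer that patients are treated at Groningen, and from this that product potency is at risk under the 8-hour limit. The text says only that they are included there. AMC-only pharmacy arrangements fit equally well with all injections being given at the AMC, so the point is conditional. A reader might also infer that an uneven split of the fMRI patients inflates the variance between arms. Section 9.2 names a before-after comparison and a comparison with healthy subjects as fMRI outcomes, not a comparison between arms.

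**Conclusion.** The point holds as a modest, inexpensive improvement, together with a contradiction to be reconciled. The single-centre label conflicts with sections 4.1 and 10.2. The primary test of section 9.2 discards the jerk-type strata of section 7.2, and section 9.3 would not bring them back.

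Under the assumed prognostic differences, the chi-square test runs at about 2 to 4% type I error instead of 5%, and a test stratified by jerk type recovers about 4 to 10 points of power. If neither factor is prognostic, nothing is lost. These figures depend on assumed response differences that the documents neither give nor exclude.

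The documents do not support a demand to make hospital a randomisation stratum. At 54 patients that is a matter of judgement, and nothing shows that patients remain to be randomised. The 4-point shift from an 11:5 hospital split is small against the planned 40-point difference and about a third of its standard error. The sample size is unaffected.

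**What to change.** 1. In section 9.2, make the primary analysis a test stratified by jerk type, for example Cochran-Mantel-Haenszel, reported with a stratified risk difference and 95% confidence interval. Keep the unstratified test as a supporting analysis.
2. Include enrolling hospital as a second stratum, or in a sensitivity analysis specified before unblinding. State in advance how sparse strata will be combined.
3. Reconcile the Summary's single-centre label with sections 4.1 and 10.2. State how many hospitals enrol and where patients entered at Groningen are injected.
4. Only if injections are given at Groningen, reconcile sections 6.7, 6.8 and 7.2 with that.

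The cost is a few sentences and slightly more analysis work. The downside is possible sparse strata, mainly if jerk type and hospital are crossed or one jerk type is rare. No change to the sample size or randomisation is needed.

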## 1. INTRODUCTION AND RATIONALE

Botulinum neurotoxin (BoNT) has emerged as a useful therapy for several movement disorders associated with muscle overactivity. When BoNT is injected in the muscles, the toxin produces local chemodenervation by blocking the release of acetelylcholine at the neuromuscular junctions. It thereby renders the muscle (partially) unable to contract for a period of 3 to 4 months. The most common side effects of BoNT are local weakness and pain. These side effects are reversible as well.

BoNT is an effective treatment for several disorders, for example for cervical dystonia and blepharospasm, diseases for which therapeutic options previously were restricted.
Botulinum toxin seems a promising therapy for other movement disorders associated with muscle overactivity as well, including jerky movement disorders. We hypothesize that BoNT is an effective treatment for jerky movement disorders of psychogenic origin.

Psychogenic movement disorders are disorders that cannot be accounted for by any known neurologic ("organic") syndrome and encompass a diversity of hyperkinetic movements. Psychogenic movement disorders are amongst the commonest of unexplained neurological symptoms and are supposed to exist in at least 2–9% of patients seen in movement disorder clinics. Of patients with psychogenic movement disorders, 22% were shown to have psychogenic jerks (myoclonus and tics). Although there are some general features common to all functional movement disorders, diagnosis may be difficult. Diagnosis of functional jerks however is largely assisted by the results of EMG and EEG. When the EEG consistently shows a characteristic pre-movement potential (Bereitschaftspotential), the diagnosis psychogenic jerks can be made quite certain.

When patients with psychogenic neurological symptoms are compared to those with symptoms associated with organic disease, they are found to have similar disability and more distress. Psychogenic movement disorders often coexist with psychiatric disease: 38% of patients were shown to have an axis I diagnosis (mostly depression and anxiety disorders) and 42% had an axis II diagnosis (personality disorder). In general, patients with psychogenic movement disorders are treated multidisciplinary by a psychiatrist, neurologist and often a physical therapist. The effects of treatment are unsatisfactory: after an interval of 3.2 – 6 years, 65 – 90% of the treated patients still has a psychogenic movement disorder. An important factor associated with poor outcome is long duration of symptoms. It is gradually becoming clear that the distinction between organic and psychogenic disorders is not as black-and-white as was previously thought. Psychogenic and organic dystonia for example share similar neurophysiologic abnormalities. Besides, it appears that abnormal sensory input from repetitive movements can produce changes in the central nervous system. It has been hypothesized that these central changes can participate in maintaining

the movement disorder (i.e. dystonia). In such a situation, treatment of the psychiatric disturbances alone may not be enough to alleviate the disorder. Treatment with BoNT might restore the changes in the central nervous system via normalisation of movement patterns. Although no studies have been published on the effect of treatment with BoNT on psychogenic movement disorders, our own clinical experience clearly suggests improvement.

Recently our research group was the first to perform an fMRI study concerning patients with psychogenic jerks in an attempt to gain more insight in the pathophysiology of this disorder (MEC# 07/290). However no imaging studies have ever been performed to evaluate treatment effect in psychogenic movement disorders. Therefore we would like to perform a functional magnetic resonance imaging study in a small sample of our patient population to evaluate the BoNT treatment and to improve knowledge on pathophysiology and diagnostics of psychogenic jerks.

## 2. OBJECTIVES

## Objectives of the randomized placebo controlled trial:

## **Primary Objective:**

To assess whether treatment with BoNT improves motor characteristics of an invalidating jerk of interest in patients with psychogenic jerks according to a movement disorder specialist.

## **Secondary Objectives:**

To asses, in patients with psychogenic jerks, the effect of treatment with BoNT on:

- · the severity of the invalidating jerk of interest scored by a movement disorder specialist;
- improvement of motor characteristics and severity of the invalidating jerk of interest scored by the patient;
- the nature, distribution and severity of overall dyskinesia, scored by a movement disorder specialist;
- the frequency of the invalidating jerk of interest;
- whether patients consider treatment with BoNT effective and whether they judge that the benefits of treatment outweigh the side-effects;
- disability;
- · quality of life;
- co-existent psychiatric disorders;
- · the occurrence of adverse reactions;
- muscle weakness;
- · difference in brain function measured by fMRI

